10.4 Dexamethasone

Dexamethasone is a synthetic adrenoglucocorticoid. It is commercially available as a generic in tablet form for oral administration. It is indicated for a variety of medical conditions, including cancer. Commercial supplies of dexamethasone will be used for this study and charged to study subjects or their insurance company.

10.4.1 Storage

Dexamethasone is to be stored at controlled room temperature 20 to 25°C (68 to 77°F). Consult the package insert of the respective product for additional storage and usage instructions.

10.4.2 Summary of Adverse Events Associated with Dexamethasone

See Reference [25] for a more complete summary. Also see Section 6.6.2, Table 14.

The side effects from systemic glucocorticoids are usually dose and duration dependent, and can impact virtually all body systems. Common side effects include thinning of the skin, purpura, Cushingoid appearance, weight gain, sleep disturbance and mood changes. Hyperglycemia is common if these agents are used in patients with pre-existing diabetes or those at risk of diabetes for other reasons. Cataracts are also common with prolonged (>1 year) of glucocorticoids. Other risks of concern with glucocorticoids include an increased risk of cardiovascular disease and hypertension (particularly when glucocorticoids are prescribed in patients with pre-existing cardiac or renal disease), increased risk of peptic ulcer disease and gastritis (especially when patients are also taking nonsteroidal anti-inflammatory agents), osteoporosis, increased fracture risk, osteonecrosis, myopathy, edema, and immunosuppression with an increased risk of infection. With the exception of cataracts and some of the cardiac and bone toxicities, adverse effects from glucocorticoids are at least partially reversible upon discontinuation.

11. DATA AND SAFETY MONITORING PLANS

11.1 Safety Monitoring

Data will be collected in electronic case report forms (eCRFs). Study personnel will be trained on data entry by the sponsor and provided protocol-specific eCRF guidelines.

This protocol will be monitored according to the processes in effect for all LCI investigator-initiated studies and will abide by applicable regulations and guidelines (e.g. Good Clinical Practice [GCP]). It is the responsibility of the Sponsor-Investigator to monitor the safety data for this study. The Sponsor-Investigator, and other sponsor-level team members will meet regularly to monitor subject consents, enrollment and retention, safety data and timeliness/ validity/integrity of the data. Documentation of these meetings will be kept with study records. The Sponsor-Investigator will submit data to the LCI Data and Safety Monitoring Committee according to the protocol-specific Data and Safety Monitoring Plan.

This study will be monitored to ensure the study is conducted in compliance with the study protocol, SOPs of the LCI and Atrium Health Office of Clinical and Translational Research (and/or other participating institutional SOPs), the FDA, and other applicable regulations and guidelines (e.g. GCP).

Investigators and/or their delegated study personnel will be required to be available during the monitoring visits.

11.2 Data Monitoring

This study will be organized, performed, and reported in compliance with the study protocol, SOPs of the LCI and AH Office of Clinical and Translational Research (and/or other participating institutional SOPs), the FDA, and other applicable regulations and guidelines (e.g. GCP).

Subjects will be monitored by LCI Research /Data Monitors per the study-specific monitoring plan and LCI/AH SOPs for data quality. This monitoring will be done by comparing source documentation to the electronic case report forms (eCRFs). Any variation between the two data sets will be discussed with the investigator, Sponsor-Investigator and/or other study team members as appropriate.

The study database will be reviewed and checked for omissions, apparent errors, and values requiring further clarification using computerized and manual procedures. Data queries requiring clarification will be generated and addressed by the appropriate study team member. Only authorized personnel will make corrections to the study database and all corrections will be documented in an electronic audit trail.

The trial site may also be subject to quality assurance audit by BMS or its designee as well as inspection by appropriate regulatory agencies.

It is important for all investigators and their relevant personnel to be available during the monitoring visits and possible audits and for sufficient time to be devoted to the process.

12. SAFETY DATA COLLECTION, RECORDING AND REPORTING

12.1 Definitions

12.1.1 Adverse Event

An adverse event is any untoward medical occurrence in a study subject who is administered any drug that does not necessarily have a causal relationship with this treatment. An adverse event can therefore be any unfavorable and unintended sign (including an abnormal laboratory finding), symptom, or disease temporally associated with the use of a medicinal product, whether or not considered related to the medicinal product. Pre-existing conditions that increase in frequency or severity or change in nature during or as a consequence of use of a drug in human clinical trials are also considered adverse events. Adverse events may also include pre- or post-treatment complications that occur as a result of protocol mandated procedures (e.g., invasive procedures such as biopsies).

An increase in grade to a pre-existing CTCAE toxicity grade present at the time of study treatment initiation will be recorded as an AE. Changes in vital signs, ECG, physical examination and laboratory test results will be recorded as an AE if they are judged clinically significant by the investigator and/or require a medical intervention or dose modification.

Any continuing medical condition or clinically significant laboratory abnormality with an onset date before the first date of study treatment administration should be considered pre-existing and should be documented.

An AE does not include:

- relapse or progression of the underlying malignant disease;
- medical or surgical procedures (e.g., surgery, endoscopy, tooth extraction, transfusion);
NOTE: the condition that leads to the procedure may be an adverse event;
- situations where an untoward medical occurrence has not occurred (e.g., hospitalization for elective surgery, social and/or convenience admissions);

The severity of adverse events should be classified and recorded according to the CTCAE version 4.03.

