6. TREATMENT DETAILS AND DOSE MODIFICATIONS/DELAYS

Any subject who receives treatment on this protocol will be evaluable for toxicity. Each subject will be assessed periodically for the development of any toxicity according to the Study Calendar. Toxicity will be assessed according to the National Cancer Institute (NCI) Common Terminology Criteria for Adverse Events (CTCAE), v4.03. Dose adjustments should be made according to the system showing the greatest degree of toxicity.

Note: In each dose modification table in Section 6, the Recommended Action is per investigator's discretion.

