6.3.4.1 Hematologic Toxicities

NOTE: Thrombocytopenia has been transient and typically resolves during the week between treatments.

Table 4: Dose Modifications for Hematologic Toxicities

Toxicity	Recommended Action
ANC < 500/mm ³	
 First occurrence: Hold dose; resume at same dose level once ANC recovers to $\geq 500/\text{mm}^3$ For any recurrence: hold dose; resume with dose reduced by 1 level once ANC recovers to $\geq 500/\text{mm}^3$
ANC < 500/mm ³ and temperature >38.5°C or 2 consecutive readings of >38.0°C for 2 hours	
 Hold dose; resume at same dose level once ANC returns to baseline and fever resolves
Platelets < 10,000/mm ³ or evidence of bleeding with thrombocytopenia	
 First occurrence: Hold dose; resume at same dose level once platelets recover to $\geq 10,000/\text{mm}^3$ and/or bleeding is controlled For any recurrence, hold dose; resume with dose reduced by 1 level once platelets recover to $\geq 10,000/\text{mm}^3$ and/or bleeding is controlled

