6.4.3.2 Other Elotuzumab-Related Toxicities (Non-IRR)

Delay elotuzumab for any \geq grade 3 toxicity (non-IRR) considered at least possibly related to elotuzumab. Treatment may resume once levels resume to baseline or \leq grade 1.

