6.5.2.1 Hematologic Toxicities

Table 12: Dose Modifications for Hematologic Toxicities

Toxicity	Recommended Action
ANC < 1000/mm ³	
 Interrupt lenalidomide Resume at same dose level once ANC recovers to $\geq 1000/\text{mm}^3$ For any recurrence, interrupt lenalidomide; resume with dose reduced by 1 level once ANC recovers to $\geq 1000/\text{mm}^3$
Platelets < 30,000/mm ³ or evidence of bleeding with thrombocytopenia	
 Interrupt lenalidomide Resume with dose reduced by 1 level once platelet count recovers to $\geq 30,000/\text{mm}^3$ For any recurrence, interrupt lenalidomide; resume with dose reduced by 1 level once platelets recover to $\geq 30,000/\text{mm}^3$

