14.3.8 Safety Endpoints

Safety endpoints will include treatment administration (cumulative dose, dose intensity, and relative dose intensity—dose intensity as a percent of intended dose intensity), AEs, SAEs, and deaths while on study therapy.

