14.5.6 Safety Analysis

Incident rates for treatment-emergent adverse events, adverse events leading to study drug discontinuation, SAEs and deaths while on study therapy will be summarized. Treatment-emergent adverse events are defined as follows:

- An adverse event that occurs after treatment start that was not present at the time of treatment start; **OR**
- An adverse event that increases in severity after treatment start if the event was present at the time of treatment start.

Cumulative doses will be calculated for each subject (for elotuzumab, carfilzomib and lenalidomide) in both absolute terms and as a percent of expected cumulative dose (relative dose intensity). Cumulative dose and relative dose intensity will then be summarized for the study arm.

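### The safety analysis plans no summary of measured blood counts, so a scheduled grade 3 or higher value, above all for lymphocytes or total WBC, can go unreported if nobody records it as an AE

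*Combined protocol and SAP*

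**What the plan says.** The Study Calendar (Section 7) schedules a blood count with differential and platelets on most visit days of induction, on day 1 of each maintenance cycle and at the Safety Follow-up Visit.

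Section 14.3.8 lists the safety endpoints as treatment administration plus "AEs, SAEs, and deaths while on study therapy". Section 14.5.6 states: "Incident rates for treatment-emergent adverse events, adverse events leading to study drug discontinuation, SAEs and deaths while on study therapy will be summarized". It then adds cumulative dose and relative dose intensity. Neither section mentions measured laboratory values.

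Two sentences in Section 12.1.1 govern how a laboratory finding becomes an AE. One reads: "An increase in grade to a pre-existing CTCAE toxicity grade present at the time of study treatment initiation will be recorded as an AE". The other covers laboratory changes among others, and its rule is that "test results will be recorded as an AE if they are judged clinically significant by the investigator and/or require a medical intervention or dose modification". Section 12.1.6 adds significant worsening on other safety assessments, without naming a grade.

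**The concern.** The counts are taken on a fixed schedule, but they enter the AE tables through a filter that has no grade threshold. A subject with a normal baseline could reach grade 3 lymphopenia on a scheduled draw, have no dose changed and no treatment given, and not be judged to have a clinically significant change. That value would then appear nowhere in the planned safety summary.

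What is at stake is how completely the hematologic toxicity of a new four-drug regimen is described. Section 1.3.4.1 reports grade 3 or 4 lymphopenia in 76.7% and leukopenia in 32.4% of the elotuzumab arm of the earlier lenalidomide-dexamethasone trial, as laboratory abnormalities. A reader who wants the comparable figure from this trial would not find it. The response endpoint and its decision rule are not involved.

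**Working it through.** The plan gives no figure to reproduce. The check is to follow each kind of scheduled value to the planned safety summary and ask what, other than a judgement of clinical significance, would put it there.

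**1. Routes by analyte**

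| Analyte | Route other than clinical significance | Where |
|---|---|---|
| ANC | Carfilzomib held below 500/mm³; lenalidomide interrupted below 1000/mm³ | 6.3.4.1, 6.5.2.1 |
| Platelets | Carfilzomib: "Platelets < 10,000/mm"³; lenalidomide: "Platelets < 30,000/mm"³; or bleeding with thrombocytopenia | 6.3.4.1, 6.5.2.1 |
| Hemoglobin | No dose trigger, but anemia is to be treated under institutional guidelines | 6.8.3 |
| Chemistries | Holds for creatinine, AST and bilirubin changes and for grade 3 or higher non-hematologic toxicity; electrolyte replacement | 6.3.4.2, 6.5.2.3 |
| Lymphocytes, total WBC | No entry in either hematologic table | 6.3.4.1, 6.5.2.1 |

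The table-based routes are softened by the note opening Section 6: "In each dose modification table in Section 6, the Recommended Action is per investigator"'s discretion. Platelets may also be partly exposed if the CTCAE grade 3 limit lies above 30,000/mm³. The documents do not print the grade limits.

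**2. The elotuzumab delay rule**

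The broadest trigger that can reach lymphocytes and WBC is in Section 6.4.3.2. It delays elotuzumab at or above "grade 3 toxicity (non-IRR) considered at least possibly related to elotuzumab". It is text rather than a table, so the discretion note does not apply, but it needs an attribution judgement.

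It can act only when a dose is due. Post-baseline induction draws: cycle 1, 3 (D8, 15, 22); cycle 2, 4 (D1, 8, 15, 22); cycles 3 and 4, 3 each (D1, 8, 15). Total 3 + 4 + 3 + 3 = 13. Of these, 3 + 4 + 1 + 1 = 9 fall on elotuzumab days. The other 4 are D8 and D15 of cycles 3 and 4, when a value that recovers by the next D1 delays nothing. In maintenance the count and the dose are both due on D1, so this timing gap closes there.

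**3. Baseline dependence**

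On one reading of Section 12.1.1, a rise over a grade already present at treatment start is recorded without any judgement, while a change from no grade goes through the filter. The same grade 3 value could then be counted in one subject and missed in another. On the other reading, the sentence specific to laboratory results governs all laboratory changes. The text does not settle which applies.

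**4. Can the two sources differ?**

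Section 10.2.5 gives both for the KRd arm (n = 392), at grade 3 or higher:

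| | As adverse reaction | By laboratory | Ratio |
|---|---|---|---|
| Neutropenia / ANC | 104/392 = 26.5% | 39% | 0.68 |
| Thrombocytopenia / platelets | 58/392 = 14.8% | 26% | 0.57 |
| Anemia / hemoglobin | 53/392 = 13.5% | 15% | 0.90 |

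Lymphopenia and leukopenia have no row in that table of reactions at 10% or more, against laboratory rates of 46% and 25%. This shows that reaction and laboratory rates can differ, and no more than that. The recording rule of that study is not given, nor is the time window of its laboratory rates.

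**The case against.** The strongest reply is that nothing promised is missing. The safety objective in Section 2.3 is drug administration, CTCAE-graded AEs, SAEs and deaths, and Sections 14.3.8 and 14.5.6 deliver these. The AE rule is coherent. Section 12.1.1 includes abnormal laboratory findings in its definition of an AE, and Section 6 requires periodic assessment for any toxicity. This stands: the point is an improvement, not the correction of an error.

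Second, a reader might infer that chemistries are as exposed as blood counts. The documents do not support this. Sections 6.3.4.2 and 6.5.2.3 hold drug for grade 3 or higher non-hematologic toxicity, and a required dose change is itself a ground for recording an AE. Dose holds for ANC and platelets also show in relative dose intensity, so AE records are not the only trace.

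Third, a reader might multiply the Section 10.2.5 rates by 40 to predict how many subjects this trial would miss. With an unknown recording rule and time window, that projection is unsupported. Section 1.3.4.2 points the other way: it lists grade 3 or higher lymphopenia as a reaction in 25% of a phase I trial, so capture can be substantial. Lymphopenia is also known to be more frequent with elotuzumab (Section 1.3.4.1), so a judgement of possible relatedness may be easily reached.

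Fourth, the eCRF guidelines and the monitoring plan mentioned in Section 11.1 are not in the documents and may govern laboratory capture. They could lower the cost of a table, but would not themselves add one to the planned analysis.

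What remains is narrow: no rule requires every grade 3 or higher count to be recorded, and no planned table shows the measured values.

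**Conclusion.** The point holds as a cheap improvement of optional priority. The planned analysis can omit scheduled grade 3 or higher blood counts. Lymphocytes and total WBC depend most on judgement; that ranking is an inference from the dose rules, not a statement in the plan.

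The size of the loss in this trial cannot be computed and may be zero. It depends on how often investigators record such values, which the documents do not give. Dependence on baseline grade is one reading of Section 12.1.1, not a settled fact.

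Nor should a reader conclude that AE rates must be the lower ones. AEs are collected to 90 days after the last dose (Section 12.3.1) and can arise from unscheduled tests, while the last scheduled count is about 30 days after treatment stops. The two sources answer different questions, and the plan reports one. The primary endpoint is unaffected.

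**What to change.** In Section 14.3.8 add:

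> Hematologic laboratory toxicity graded by CTCAE v4.03 from measured values.

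In Section 14.5.6 add:

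> For lymphocytes, WBC, ANC, platelets and hemoglobin, the worst post-baseline CTCAE grade during induction will be tabulated against baseline grade, with number and percent of subjects at grade 3 or higher, whether or not an AE was recorded, and shown beside the AE table.

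Leave Section 12.1.1 unchanged. Extend the table to maintenance, the Safety Follow-up Visit and chemistries only if those values are already in the eCRF.

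No new tests are needed, and AE rates do not change. If the values are in the eCRF, the cost is programming; the documents do not show whether they are. If not, data entry for 40 subjects is 13 draws × 40 × 5 analytes = 2,600 post-baseline values, or 14 × 40 × 5 = 2,800 with one baseline set. Each maintenance cycle would add up to 40 × 5 = 200 more, which is why the table is limited to induction.

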12.1.2 Suspected Adverse Reaction (SAR)

A suspected adverse reaction (SAR) is any AE for which there is a *reasonable possibility* that the drug is the cause. *Reasonable possibility* means that there is evidence to suggest a causal relationship between the drug and the AE. A suspected adverse reaction implies a lesser degree of certainty about causality than adverse reaction, which means any adverse event caused by a drug.

Causality assessment to a study drug is a medical judgment made in consideration of the following factors: temporal relationship of the AE to study drug exposure, known mechanism of action or side effect profile of study treatment, other recent or concomitant drug exposures, normal clinical course of the disease under investigation, and any other underlying or concurrent medical conditions. Other factors to consider in considering drug as the cause of the AE:

- Single occurrence of an uncommon event known to be strongly associated with drug exposure (e.g., angioedema, hepatic injury, Stevens-Johnson Syndrome)
- One or more occurrences of an event not commonly associated with drug exposure, but otherwise uncommon in the population (e.g., tendon rupture); often more than once occurrence from one or multiple studies would be needed before the Sponsor-Investigator could determine that there is *reasonable possibility* that the drug caused the event.
- An aggregate analysis of specific events observed in a clinical trial that indicates the events occur more frequently in the drug treatment group than in a concurrent or historical control group

12.1.3 Adverse Reaction

An adverse reaction means any adverse event caused by a drug. Adverse reactions are a subset of all suspected adverse reactions where there is reason to conclude that the drug caused the event.

12.1.4 Serious AE or SAR

An AE or SAR is to be considered serious if the investigator deems it as such and the event results in any of the following outcomes:

- Death (fatal);
- Life-threatening situation (subject is at immediate risk of death);
- Persistent or significant disability/incapacity;
- Requires or prolongs inpatient hospitalization¹;
- A congenital anomaly/birth defect in the offspring of a subject who received study drug;
- Based upon appropriate medical judgment, may jeopardize the subject and may require medical or surgical intervention to prevent one of the afore listed outcomes from occurring (e.g. intensive treatment in an emergency room without hospitalization, blood dyscrasias or convulsions that do not result in hospitalization, development of drug dependency or drug abuse). **NOTE:** Potential drug induced liver injury (DILI²) is also considered an important medical event.
- Suspected transmission of an infectious agent (e.g., pathogenic or nonpathogenic) via the study drug is an SAE.
- Although pregnancy³, overdose⁴, and cancer are not always serious by regulatory definition, these events must be handled as SAEs.

¹Hospitalizations for study drug administration, protocol-related procedures, palliative or hospice care, or placement of an indwelling catheter, unless associated with other serious events, will not be recorded as SAEs. Other hospitalizations planned at the beginning of the trial also do not need to be reported as an SAE.

²Potential Drug Induced Liver Injury (DILI)

Wherever possible, timely confirmation of initial liver-related laboratory abnormalities should occur prior to the reporting of a potential DILI event. All occurrences of potential DILIs, meeting the defined criteria below must be reported as SAEs. Potential DILI is defined as

1. ALT or AST elevation > 3 X ULN **AND**
2. Total bilirubin > 2 X ULN, without initial findings of cholestasis (elevated serum alkaline phosphatase) **AND**
3. No other immediately apparent possible causes of AST/ALT elevation and hyperbilirubinemia, including, but not limited to, viral hepatitis, pre-existing chronic or acute liver disease, or the administration of other drug(s) known to be hepatotoxic.

³Pregnancy

If, following initiation of study treatment, it is subsequently discovered that a study subject is pregnant or may have been pregnant at the time of study treatment exposure, including during at least 5 half-lives after product administration, the pregnancy must be reported as an SAE.

⁴Overdose

An overdose is defined as the accidental or intentional administration of any dose of a product that is considered both excessive and medically important. All occurrences of overdose must be reported as an SAE.

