12.3.3 SAEs

All SAEs, whether related to study treatment or not, including those thought to be associated with protocol-specified procedures, will be collected. SAEs will be reported after informed consent and continuing through 90 days after the discontinuation of all protocol mandated therapy. If the subject initiates subsequent anti-cancer therapy prior to 90 days after cessation of study treatment, the reporting period is through 60 days following cessation of study treatment or until the start of the subsequent anti-cancer therapy, whichever is later. Any SAE occurring after these time periods that is believed to be related to study drug(s) or protocol-specified procedure should also be reported.

It is the responsibility of the Sponsor-Investigator, investigators and the protocol team to ensure SAEs are reported according to the Code of Federal Regulations (CFR), GCP, the protocol guidelines, IRB, and FDA policy.

SAEs will be followed until clinical recovery is complete and laboratory tests have returned to baseline, until progression has been stabilized, or until there has been acceptable resolution of the event. This may at times cause the follow-up period for SAEs to be greater than 90 days. Similarly, the Sponsor-Investigator is responsible for following the subject during the required follow-up period even if the subject lives elsewhere or has been released from his or her care and is being treated under another service at LCI.

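### Section 12.1.4 makes SAE status depend on the investigator's opinion as well as a listed outcome, so a qualifying event can be left out of SAE reporting and the SAE rate

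*Combined protocol and SAP*

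**What the plan says.** The lead-in to the SAE definition in 12.1.4 states that an adverse event or suspected reaction "is to be considered serious if the investigator deems it as such and the event results in any of the following outcomes". The outcomes that follow include death, a life-threatening situation, persistent or significant disability, and an event that "Requires or prolongs inpatient hospitalization" (with the exclusions in footnote 1). There is also an item for important medical events, which carries its own appeal to medical judgement.

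Some items in the same section are worded without reference to the investigator's view:

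- Suspected transmission of an infectious agent "via the study drug is an SAE".
- For pregnancy, overdose and cancer, "these events must be handled as SAEs".
- For liver injury, "All occurrences of potential DILIs, meeting the defined criteria below must be reported as SAEs".

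The later sections take SAE status as given. Section 12.3.3 says: "All SAEs, whether related to study treatment or not, including those thought to be associated with protocol-specified procedures, will be collected". Section 12.3.3.1 asks for SAEs to reach the Sponsor-Investigator within one business day. Section 12.3.3.2 asks for them to reach the manufacturer within 24 hours of the Sponsor-Investigator's awareness. Section 12.3.4 sends SAEs and unanticipated problems (UAPs) to the IRB. Section 14.5.6 summarizes SAE rates without a definition of its own.

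**The concern.** A list of outcomes normally settles seriousness by what happened to the subject. Here the lead-in adds a second necessary condition, the investigator's opinion. The list already has a place for judgement in the important-medical-event item, so for the other outcomes the added clause can act only as a veto.

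At stake are prompt reporting, the SAE route to the IRB, follow-up of SAEs to resolution under 12.3.3, and the SAE rate that readers will use to judge the tolerability of adding elotuzumab to KRd. The trial is single-arm and open-label, with no planned interim analysis (14.5.7) and no numerical toxicity boundary in the protocol. Safety oversight therefore rests on review of reported events (11.1), and 15.2 names SAEs as an example of a finding that could end the study. There is no concurrent arm against which under-classification would show.

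**Working it through.** The plan states no figure on this point, so the check is a comparison of sections.

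**Step 1: which events depend on the clause.** Let D be the events with a listed outcome, J the events the investigator deems serious, and A the items made SAEs by their own wording. As written, SAEs are (D and J) or A. If a listed outcome were sufficient, SAEs would be D or A. The difference is the events in D that are in neither J nor A.

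A contains suspected infectious transmission, pregnancy, overdose, cancer and potential drug-induced liver injury (12.1.4), and abnormal pregnancy outcomes including congenital anomaly (12.3.2). That leaves death, life-threatening situations, disability and hospitalization exposed. Because (D and J) can never be larger than D, the condition can lower the SAE count but not raise it.

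**Step 2: whether a later rule restores these events.**

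- Sponsor-Investigator and manufacturer reporting (12.3.3.1, 12.3.3.2) set aside relatedness and expectedness, but only for events already classed as SAEs. The seriousness test is not set aside.
- Life-threatening complications and UAPs must be notified to the Sponsor-Investigator at once by email (12.3.3.1), whatever their SAE status. Manufacturer reporting and the SAE count have no such rule.
- Unexpected events, serious or not (12.1.5), qualify as UAPs under 12.1.7 and so reach the Sponsor-Investigator and the IRB. Expected events do not qualify by this route.
- FDA notice within 7 days (12.3.5) is triggered by outcome, for unexpected fatal or life-threatening events possibly related to study drug. The 15-day category uses the word serious and so inherits the definition.
- Deaths on study therapy are summarized separately (14.5.6). A death not deemed serious would leave the SAE count but not the death count.
- AEs are recorded with grade, dates and attribution (12.3.1), so most such events stay in the AE data. The windows differ, however. AE collection starts on day 1 of treatment and SAE collection at consent. If new anti-cancer therapy starts within 30 days of stopping treatment, the AE window closes at day 30 and the SAE window at day 60. In those 60 − 30 = 30 days, and between consent and day 1, an event not deemed serious need not be collected.

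**Step 3: what remains.** Expected hospitalization and disability have the fewest safeguards. These are not rare categories for this drug: 10.1.9 lists pneumonia and pyrexia among the expected serious reactions, and 1.3.4.1 gives them as the two most frequent serious reactions in the elotuzumab arm of the phase III trial with Rd (15.4% and 6.9%). Life-threatening events remain exposed for manufacturer reporting and the SAE tally.

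**Step 4: size.** The subject-level loss would require the share of qualifying events not deemed serious and how those events cluster within subjects. The documents give neither. A subject with several qualifying events drops out of the SAE proportion only if none of them is deemed serious, so an event-level omission rate does not carry over to subjects.

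**The case against.** The best defence is that the rest of Section 12 covers the gravest cases. Life-threatening complications go to the Sponsor-Investigator immediately, faster than the SAE timetable. Unexpected events travel as UAPs, the seven-day FDA notice depends on outcome, and deaths are tabulated separately. Monitors compare source documents with the eCRFs (11.2) and could query an unclassified hospitalization. Sections 12.3.3 and 12.3.5 also require reporting in line with federal regulations and GCP, and 12.1.4 alludes to a regulatory definition of seriousness. No pre-specified test or boundary uses the SAE count; the primary decision rule is 21 of 40 subjects with VGPR or better. In practice many investigators may apply the outcome list alone.

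Most of this stands, and it narrows the reach. It does not remove the defect. None of these provisions says that a listed outcome suffices for SAE status. The text of the regulatory definition is not in the protocol. A monitor checking against 12.1.4 as written would find nothing to correct.

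Two stronger readings should be resisted. A reader might infer that 12.1.4 contradicts itself, because pregnancy, overdose, cancer and liver injury are SAEs without the investigator clause. The text does not support that: those items are explicit additions to a conditional definition. They are also not free of judgement, since overdose must be regarded as medically important and potential liver injury requires that no other cause be apparent. A reader might also infer that prompt notice of life-threatening events is lost altogether. Sections 12.3.3.1 and 12.3.5 show otherwise.

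**Conclusion.** The point holds in a limited form. As written, a listed outcome is necessary but not sufficient for seriousness, so an event meeting one can be kept out of SAE reporting and the SAE rate. The exposure is mainly expected hospitalization and disability, and life-threatening events for manufacturer reporting and the SAE tally. This rests on the plain reading of the conjunction. If the intent was only that the investigator judges whether an outcome occurred, the text does not say so.

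The direction is certain (the SAE count can only fall) and the size is unknown. A reader might be tempted to apply the 65.4% serious-reaction rate in 1.3.4.1 to 40 subjects (0.654 × 40 = 26.2) and take off a percentage. The documents do not support that: the rate belongs to a different regimen, no omission rate is given anywhere, and an omission rate for events is not one for subjects. The primary efficacy analysis is unaffected.

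**What to change.** In the lead-in to 12.1.4, delete the clause that makes seriousness conditional on the investigator's view, together with its conjunction, so that an event is serious if it results in any listed outcome. Keep medical judgement in the important-medical-event item, and leave the hospitalization exclusions in footnote 1 unchanged. No change to treatment, endpoints, sample size or the wording of 12.3 and 14.5.6 is needed, because those sections take the definition from 12.1.4.

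The cost is one phrase in an amendment and possibly a slightly higher SAE count. AEs already recorded with a listed outcome but not classed as SAEs could be checked once against the corrected definition, so that the SAE rate in 14.5.6 rests on one rule throughout.
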